## 2.2 Trial Diagram

## 3.0 OBJECTIVE(S) & HYPOTHESIS(ES)

### 3.1 Primary Objective(s) & Hypothesis(es) (safety run in-phase)

(1) **Objective:** Determine the safe and tolerable dose of AZA followed by pembrolizumab in relapsed and refractory AML patients.

**Hypothesis:** AZA followed by pembrolizumab will be safe and tolerable in relapsed and refractory AML.

### 3.2 Primary Objective(s) & Hypothesis(es) (Phase 2)

(1) **Objective (Cohort 1):** Estimate the complete remission (CR/CRi) rate of AZA followed by pembrolizumab in relapsed and refractory AML patients.

**Hypothesis:** AZA followed by pembrolizumab will be effective (CR/CRi) in relapsed and refractory AML.

(2) **Objective (Cohort 2):** Estimate the complete remission (CR/CRi) rate of AZA followed by pembrolizumab in older (≥65 years) newly diagnosed AML patients not candidates for intensive induction chemotherapy.

**Hypothesis:** AZA followed by pembrolizumab will be effective (CR/CRI) in older ( $\geq 65$  years) newly diagnosed AML patients not candidates for intensive induction chemotherapy.

### 3.3 Secondary Objective(s) & Hypothesis(es)

(1) **Objective (Cohort 1):** Characterize the toxicity of AZA followed by pembrolizumab in relapsed and refractory AML.

**Hypothesis:** AZA followed by pembrolizumab will be safe and tolerable when administered to relapsed and refractory AML patients.

(2) **Objective (Cohort 2):** Characterize the toxicity of AZA followed by pembrolizumab in older ( $\geq 65$  years) newly diagnosed AML patients not candidates for intensive induction chemotherapy.

**Hypothesis:** AZA followed by pembrolizumab will be safe and tolerable when administered to older ( $\geq 65$  years) newly diagnosed AML patients not candidates for intensive induction chemotherapy.

(3) **Objective (Cohort 1):** Assess the overall response rates [ie. CR/CRI/partial response (PR)/morphologic leukemia-free state (MLFS)/hematologic improvement (HI)] of AZA followed by pembrolizumab in relapsed/refractory AML patients.

**Hypothesis:** AZA followed by pembrolizumab will lead to a promising overall response rate in relapsed and refractory AML patients.

(4) **Objective (Cohort 2):** Assess the overall response rates [ie. CR/CRI/partial response (PR)/morphologic leukemia-free state (MLFS)/hematologic improvement (HI)] of AZA followed by pembrolizumab in newly diagnosed AML patients not candidates for intensive induction chemotherapy.

**Hypothesis:** AZA followed by pembrolizumab will lead to a promising overall response rate in older ( $\geq 65$  years) newly diagnosed AML patients not candidates for intensive induction chemotherapy.

(5) **Objective (Cohort 1 and Cohort 2):** Estimate disease-free survival (DFS) and overall survival (OS) of patients who achieve a CR/CRI for each cohort separately: relapsed/refractory (Cohort 1) and newly diagnosed older AML patients (Cohort 2).

**Hypothesis:** Patients who achieve a CR/CRI will have durable responses.

(6) **Objective (Cohort 1 and Cohort 2):** Estimate progression-free survival (PFS), time to progression (TTP), and OS for all patients. These survival parameters will be estimated separately for each Cohort.

**Hypothesis:** AZA followed by pembrolizumab will lead to a promising PFS, TTP and OS in both relapsed/refractory and older newly diagnosed AML patients not candidates for intensive induction chemotherapy.

### 3.4 Exploratory Objective

(1) **Objective:** Explore association between potential biomarkers and clinical activity of the combination of AZA and pembrolizumab in patients with relapsed and refractory AML and in older ( $\geq 65$  years) newly diagnosed AML patients not candidates for intensive induction chemotherapy.

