c During cycle 1 and 2, patients will have laboratory tests weekly. However, patients may have laboratory tests more frequently (twice or more per week) as needed according to standard of care for management of patients with AML as determined and at the discretion of the investigator/treating physician. In subsequent cycles, patient is required to have laboratory tests on day 1 and days of pembrolizumab administration in that cycle. However, patients may have laboratory tests more frequently (once or more per week) as needed according to standard of care for management of patients with AML as determined and at the discretion of the investigator/treating physician.

dBone marrow aspirate and biopsy will be done as per standard of care: pre-treatment, after the completion of cycle 2, cycle 6, and every 3 months thereafter (up to 1 yr). If necessary (in the absence of count recovery as defined in Section 5.2.1.3 and 5.2.1.5.2) bone marrow as per standard of care will be done after cycle 1. In a second year, bone marrow aspirate and biopsy can be performed every 4-6 months and at the end of treatment. Bone marrow aspirate and biopsies will be performed every 4-6 months in a follow up phase. Bone marrow aspirate and biopsies can be performed at any time to evaluate for hematologic toxicity (Section 5.2.1.5.3) or if disease progression/relapse is suspected either during treatment or in follow up, or at treatment discontinuation. Each bone marrow should include morphologic assessment (aspirate/biopsy), flow cytometry, and karyotype

and/or molecular study if indicated. If karyotype was performed within 3 months prior to day 1 of treatment, it does not need to be repeated pre-treatment.

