cFor peripheral blood samples for research, 5x8.5mL light yellow top ACD tubes (or 4x10mL green top heparin tubes) of blood (~40mLs) will be collected pre-treatment on D1 of cycle 1 (for cycle 1 sample can be collected any time within 14 days prior to treatment) and cycle 2, on D8 of cycle 1 and D22 of cycle 2 (or on days of pembrolizumab administration in either cycle). Starting with cycle 3, peripheral blood samples will be collected only on day 1 of every other cycle (Cycle 3, 5, etc), at the time of the follow up visits. All samples should be collected prior to azacitidine/pembrolizumab administration if on a treatment day. Repeat blood sample at any time if there is a suspicion of leukemia recurrence either during maintenance phase or in follow-up, or at treatment discontinuation.

fThe schedule of bone marrow procedures performed according to standard of care is delineated under d. Each time a bone marrow biopsy is done as per standard of care, additional ~40 mL of bone marrow will be collected in 5x8.5mL light yellow top ACD tubes (or 4x10mL green top heparin tubes).).

gWeight should be recorder only prior to start of each Cycle. Vital signs including temperature, pulse, respiratory rate, and blood pressure will be checked immediately before pembrolizumab infusion.

hPregnancy test will be repeated every 3 cycles in women of childbearing potential.

iThyroid function monitoring every 3 cycles.

jThis applies only to patients who completed treatment and were not taken from study for progressive disease and did not start any other treatment.

kIf an echocardiogram was conducted within the 3 months prior to the screening date and the patient has not received any chemotherapy in the time between and has not experienced any cardiac symptoms or events (heart attack, chest pain, arrhythmia, etc), then the screening echocardiogram does not need to be repeated, unless it is clinically indicated per investigator's discretion.

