### **7.1.2.6 Assessment of Disease**

Bone marrow aspirate and biopsy and peripheral blood counts will be used to assess disease as per the Trial Flow Chart. Response will be assessed by standard international criteria proposed by the European LeukemiaNet Guidelines (update 2017) in AML and by IWG Modified Response Criteria (2006) for MDS (for definition of HI).

Complete remission (CR): Bone marrow blasts <5%; absence of circulating blasts or blasts with Auer rods; absence of extramedullary disease; absolute neutrophil count  $\geq$ 1,000/mcL; platelet count  $\geq$ 100,000/mcL.

Complete remission with incomplete recovery (CRi): All CR criteria except for residual neutropenia (<1,000/mcL) or thrombocytopenia (<100,000/mcL).

Complete remission without minimal residual disease (MRD): If studied pre-treatment, CR with negativity for a genetic marker by realtime quantitative polymerase chain reaction (RT-qPCR), or CR with negativity by multi-color flow cytometry. Sensitivities vary by marker tested, and by method used. Since this study does not use centralized laboratory, MRD status will be recorded if available for each patient that achieves CR or CRi.

Morphologic leukemia-free state (MLFS): Bone marrow blasts <5%; absence of blasts with Auer rods; absence of extramedullary disease; no hematologic recovery required (marrow should not be merely aplastic (marrow should not be merely “aplastic”; at least 200 cells should be enumerated or cellularity should be at least 10%).

Partial response (PR): bone marrow blasts 5-25% and decrease of pretreatment bone marrow blast % by >50%; all hematologic criteria of CR.

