#### 7.1.3.1.3.5 DNA Sequencing and Gene expression profiling

Bone marrow aspirates will be used to perform RNA sequencing, or to examine mRNA gene expression by gene array technology and/or quantitative real-time polymerase chain reaction (qPCR) to detect expression of selected immune related genes before and after treatment. In addition, whole or targeted exome sequencing on the leukemia cells may be performed (lymphocyte control) for detection of immunogenic neoepitopes.

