### **8.2.5 Analysis of Correlative Endpoints**

We will perform multi-color flow cytometry on PB and BM specimens before and after AZA and AZA/pembrolizumab treatment using three pre-determined panels of mAbs including but not limited to those specific for CD3, CD4, CD8, PD-1, CD45RA, CCR7, CD27, CD28, Ki-67, T-bet, CD127, CD25, FoxP3, HLA-DR, CTLA-4, TNFRII, ICOS, TIM3, LAG-3, CD160, 2B4, BTLA, KLRG-1, CD16, CD14, and CD56. The analyses of pre- and post-treatment PB and BM specimens for immune parameters will be descriptive and graphical in nature. Data will be summarized for each cohort separately. The change in flow values at each time point after AZA and AZA/pembrolizumab relative to the baseline value will be checked for skewness and log-transformed as appropriate. The changes will be modeled using mixed-effects, linear regression models that included fixed effects for time and a random effect for the patient to account for within-patient correlation of measurements. To explore potential differences in the change in flow values across patient subgroups, interaction terms will be included in the regression models. Post-treatment PD changes in gene expression and methylation in immune gene signaling circuits in tumor biopsies and PB will be summarized with descriptive statistics and correlated with clinical outcomes.

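### Section 8.2.5 correlates gene-expression change in unsorted marrow with clinical outcome without allowing for blast content, which both shifts that signal and defines CR/CRi

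*Combined protocol and SAP*

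**What the plan says.** Section 3.4 states the aim only as an association between markers and activity: "Explore association between potential biomarkers and clinical activity of the combination of AZA and pembrolizumab". The operative sentence is in Section 8.2.5: "Post-treatment PD changes in gene expression and methylation in immune gene signaling circuits in tumor biopsies and PB will be summarized with descriptive statistics", and these changes are also to be "correlated with clinical outcomes". The clinical outcomes are not named.

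The relevant sampling and assay provisions are:

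- **Marrow timing (Section 6.1, footnote d).** "Bone marrow aspirate and biopsy will be done as per standard of care: pre-treatment, after the completion of cycle 2, cycle 6", and at intervals after that.
- **Source of research marrow (Section 6.1, footnote f).** "Each time a bone marrow biopsy is done as per standard of care, additional ~40 mL of bone marrow will be collected". The research aspirate and the response marrow come from one procedure.
- **Response (Section 7.1.2.6).** "Complete remission (CR): Bone marrow blasts <5" (per cent), plus other criteria. CRi keeps the blast criterion and relaxes only count recovery.
- **Expression assay (Section 7.1.3.1.3.5).** "Bone marrow aspirates will be used to perform RNA sequencing, or to examine mRNA gene expression by gene array technology" or by qPCR. No sorting step is stated. Section 11.4 describes density-gradient separation of mononuclear cells, with no removal of blasts.
- **T-cell assays.** Section 7.1.3.1.3.3 isolates CD4+ and CD8+ cells before measuring methylation. Section 7.1.3.1.3.1 reads co-inhibitory markers within T-cell subsets.

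Section 8.2.5 has no blast-percentage term, no non-blast or T-cell denominator and no rule on whether a sample must precede response. The one model it specifies, for flow values, has time, a patient effect and subgroup interactions.

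**The concern.** A bulk expression value is an average over all cells in the tube. If blasts are 40% of the cells before treatment and 4% after, every transcript made by other cells gains share and every transcript made by blasts loses share, although no immune cell has changed. The same fall in blasts moves the patient into CR/CRi. For this readout, marker change and response are partly one measurement, so some correlation is to be expected when the drugs have no immune effect.

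Unsorted blood has the same problem in patients with circulating blasts, because CR/CRi also requires those to be absent.

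Section 4.2.3.2 sets out what the correlative data are for: explaining T-cell dysfunction, finding candidate predictive markers and identifying new pathways to target. A marker that merely tracks blast clearance could be carried forward for any of these.

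**Working it through.** **No plan figure to reproduce.** The documents give no sample size, test or error rate for the biomarker analysis.

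**Inputs from the documents**

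- Maximum cohort size 40 (Section 8.2.2).
- Cohort 1 null and expected CR/CRi rates 0.10 and 0.25 (Section 8.2.2), so 0.10 × 40 = 4 or 0.25 × 40 = 10 responders.
- Entry blasts at least 5% in Cohort 1 and at least 20%, in marrow and/or blood, in Cohort 2 (Section 5.1.2).
- Blasts below 5% for CR and CRi (Section 7.1.2.6).

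**Inputs assumed**

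- Baseline blast distribution, between-patient noise in the marker change, and a fixed mix of cells within the non-blast fraction. The documents give none of these.

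**Step 1: dilution alone.** Let b0 and b1 be the blast fractions before and after treatment. A signal carried only by non-blast cells is proportional to 1 − b, so

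fold change = (1 − b1) / (1 − b0).

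With b1 = 0.04:

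| Baseline blasts | Calculation | Fold change |
|---|---|---|
| 5% | 0.96 / 0.95 | 1.01 |
| 20% | 0.96 / 0.80 | 1.20 |
| 40% | 0.96 / 0.60 | 1.60 |
| 70% | 0.96 / 0.30 | 3.20 |

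A patient whose blasts do not change has a fold change of 1.00. A transcript made only by blasts scales as b1 / b0: from 40% to 4% this is 0.04 / 0.40 = 0.10, a tenfold fall. The sign of the artefact therefore depends on the transcript.

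**Step 2: how often this would pass for an association.** Null simulation: 40 patients, 4 or 10 responders, no immune effect in anyone, non-responders' blasts varying by up to 30% of baseline. Marker change = log2[(1 − b1)/(1 − b0)] + noise, noise SD 0.5 to 1.5. Responders and others are compared by t-test at two-sided 5%.

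- Baseline blasts uniform on 5-30%: false association in about 6-26% of trials.
- Baseline blasts uniform on 5-80% or 20-80%: about 19-99%.

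A separate run used the Mann-Whitney test, 10 or 14 responders and natural-log SD 0.3-0.8. It gave 8-37% for baselines of 5-30% and 67-99% for 20-80%. Measures taken within gated or sorted T cells stayed at 4-5%.

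**Step 3: comparing corrections.**

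- *Null error.* Dividing by the non-blast fraction and adjusting for its change both hold error at about 4-6%. This is partly built in, because the simulated marker is the dilution term plus noise and the fraction is taken as known exactly.
- *Power.* For a true difference of one log2 unit, SD 1 and 10 responders, the denominator keeps power near 75%. The covariate lowers it to about 37-50%, because blast change is nearly the response itself.

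**The case against.** The strongest case against runs as follows.

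1. **The scope is narrow.** Section 8.2.5 correlates only gene expression and methylation with outcomes. The methylation assay described uses isolated T cells, the co-inhibitory markers are read within T-cell subsets, and the immunohistochemistry counts are not among the readouts that Section 8.2.5 correlates. Bulk RNA is mainly what is left, and Section 4.2.3.2 treats it as optional, though Section 7.1.3.1.3.5 is firmer. This stands and limits the point to unsorted samples.
2. **The size rests on assumptions.** It does. For patients entering near 5% blasts the effect almost vanishes.
3. **Correction has a price.** Blast-change adjustment removes real signal. Moreover, the clinical blast count need not match the research tube, which is an additional, gradient-separated draw. Both stand and shape the fix.
4. **Better samples already exist.** Section 6.1 schedules blood on C1D1, C1D8, C2D1 and C2D22, and a cycle 2 marrow can precede a later response. True, but Section 8.2.5 does not say that these carry the analysis.
5. **The analysis is exploratory.** The immune-parameter analyses are called descriptive, and no test against CR/CRi is specified, so the 5% test above is a yardstick only. This lowers the severity. It does not remove a systematic bias, which a plot shows as readily as a p-value.

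A reader might go further and infer that responders will look immune-activated across all marrow markers. The documents do not support that. Blast-expressed transcripts would fall, the blood-count recovery required for CR implies returning normal haematopoiesis that can dilute T cells, and the T-cell assays escape dilution. A reader might also infer that the plan commits an immortal-time error. Section 8.2.4 does run PFS and OS from study initiation, but no section models them against an on-treatment marker change. That is a gap to close, not a planned error.

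**Conclusion.** The point holds for gene expression in unsorted marrow, and for unsorted blood with circulating blasts. Followed as written, Section 8.2.5 can report an association with CR/CRi that blast clearance alone produces, in either direction.

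The false-association rate runs from near nominal when baseline blasts are low to near certainty when they reach 80% and noise is small. Those rates depend on the assumed blast distribution, noise and fixed non-blast mix, so they are a plausible range, not a forecast. The fold changes need only the last assumption.

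The primary CR/CRi analysis and the sample size are untouched. Severity is minor: a cheap improvement to an exploratory objective.

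**What to change.** Add three statements to Section 8.2.5.

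1. **Association with CR/CRi** rests primarily on baseline samples and on samples drawn before response is declared, using the C1D1, C1D8, C2D1 and C2D22 blood already collected. Check dates patient by patient, since Section 6.1 allows a marrow after cycle 1 in some cases.
2. **Changes in unsorted samples**, including that early blood, are expressed relative to T-cell or non-blast content, using flow cytometry on the same material where available. Report the blast percentage beside each result. Use adjustment for blast change only as a sensitivity analysis, because it also removes real signal.
3. **Where a marker change is related to OS, PFS or DFS**, time is counted from the sample date among patients still event-free. This adds little if only sampled patients are compared at a common time, but it removes the ambiguity.

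The cost is wording and a little more analysis, with no new samples. Some precision is lost through error in the denominator and through patients who have an event before the sample.

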## 4.0 BACKGROUND & RATIONALE

### 4.1 Background

#### 4.1.1 Pharmaceutical and Therapeutic Background

##### 4.1.1.1 Pembrolizumab

The importance of intact immune surveillance in controlling outgrowth of neoplastic transformation has been known for decades. Accumulating evidence shows a correlation between tumor-infiltrating lymphocytes (TILs) in cancer tissue and favorable prognosis in various malignancies. In particular, the presence of CD8+ T-cells and the ratio of CD8+ effector T-cells / FoxP3+ regulatory T-cells seems to correlate with improved prognosis and long-term survival in many solid tumors.

The PD-1 receptor-ligand interaction is a major pathway hijacked by tumors to suppress immune control. The normal function of PD-1, expressed on the cell surface of activated T-cells under healthy conditions, is to down-modulate unwanted or excessive immune responses, including autoimmune reactions. PD-1 (encoded by the gene Pdcd1) is an Ig superfamily member related to CD28 and CTLA-4 which has been shown to negatively regulate antigen receptor signaling upon engagement of its ligands (PD-L1 and/or PD-L2). The structure of murine PD-1 has been resolved. PD-1 and family members are type I transmembrane glycoproteins containing an Ig Variable-type (V-type) domain responsible for ligand binding and a cytoplasmic tail which is responsible for the binding of signaling molecules. The cytoplasmic tail of PD-1 contains 2 tyrosine-based signaling motifs, an immunoreceptor tyrosine-based inhibition motif (ITIM) and an immunoreceptor tyrosine-based switch motif (ITSM). Following T-cell stimulation, PD-1 recruits the tyrosine phosphatases SHP-1 and SHP-2 to the ITSM motif within its cytoplasmic tail, leading to the dephosphorylation of effector molecules such as CD3 $\zeta$ , PKC $\theta$  and ZAP70 which are involved in the CD3 T-cell signaling cascade. The mechanism by which PD-1 down modulates T-cell responses is similar to, but distinct from that of CTLA-4 as both molecules regulate an overlapping set of signaling proteins. PD-1 was shown to be expressed on activated lymphocytes including peripheral CD4+ and CD8+ T-cells, B-cells, Tregs and Natural Killer cells. Expression has also been shown during thymic development on CD4-CD8- (double negative) T-cells as

well as subsets of macrophages and dendritic cells. The ligands for PD-1 (PD-L1 and PD-L2) are constitutively expressed or can be induced in a variety of cell types, including non-hematopoietic tissues as well as in various tumors. Both ligands are type I transmembrane receptors containing both IgV- and IgC-like domains in the extracellular region and contain short cytoplasmic regions with no known signaling motifs. Binding of either PD-1 ligand to PD-1 inhibits T-cell activation triggered through the T-cell receptor. PD-L1 is expressed at low levels on various non-hematopoietic tissues, most notably on vascular endothelium, whereas PD-L2 protein is only detectably expressed on antigen-presenting cells found in lymphoid tissue or chronic inflammatory environments. PD-L2 is thought to control immune T-cell activation in lymphoid organs, whereas PD-L1 serves to dampen unwarranted T-cell function in peripheral tissues. Although healthy organs express little (if any) PD-L1, a variety of cancers were demonstrated to express abundant levels of this T-cell inhibitor. PD-1 has been suggested to regulate tumor-specific T-cell expansion in subjects with melanoma (MEL). This suggests that the PD-1/PD-L1 pathway plays a critical role in tumor immune evasion and should be considered as an attractive target for therapeutic intervention.

Pembrolizumab is a potent and highly selective humanized monoclonal antibody (mAb) of the IgG4/kappa isotype designed to directly block the interaction between PD-1 and its ligands, PD-L1 and PD-L2. Keytruda™ (pembrolizumab) has recently been approved in the United States for the treatment of patients with unresectable or metastatic melanoma and disease progression following ipilimumab and, if BRAF V600 mutation positive, a BRAF inhibitor.

